A sentinel cohort of 12 patients (6 receiving HepTcell and 6 placebo) will undergo blinded safety review by the Safety Committee 7 to 10 days after all ongoing patients in the sentinel cohort have completed the respective dose of study medication and will determine the decision to continue at that dose to the expanded cohort. Safety will be assessed in the sentinel cohort before each dose is administered to the expanded cohort. If any of the Stopping Rules in Section 7.1.1 are met in one or more patients and the event(s) is deemed possibly or probably related to HepTcell, dosing will be suspended pending DMC review. DMC recommendations may include instituting modifications to ensure the safety of continued dosing or discontinuing the study. If none of the Stopping Rules are met, randomization and dosing may continue in the expanded study cohort. Patients will be unblinded as necessary to assess the relationship between the study medication and events that meet criteria for Stopping Rules.

Safety laboratory testing (Table 3), including liver panel, for Doses 1 and 2 will be obtained during the visits conducted 7±2 days after these doses of study medication. Safety laboratory testing following Doses 3, 4 and 5 will be obtained in the interval from 7 days after dose administration and before the next dose of study medication is administered. Safety labs after Dose 6 will be assessed at the Day 169 visit. Investigators will review the eligibility of all patients prior to dosing to determine if the next treatment is to be administered. Eligibility for the next treatment will include: 1) confirmation that patients did not meet a Stopping Rule (Section 7.1.1); 2) confirmation that the pre-treatment liver parameters are within acceptable ranges for treatment (below); 3) confirmation that patients do not have a new confirmed or suspected IMC (Appendix 2). Patients not meeting these criteria will not be treated.

If abnormalities of ALT, AST, total bilirubin, direct bilirubin, or international normalized ratio (INR) are reported after dosing is commenced, the following monitoring and dosing rules will be applied:

Toxicity	Management	Discontinuation of Study Medication
ALT or AST \geq 5×but < 10 × ULN, and Total and direct bili < 1.5×ULN, and INR < 1.3 ×ULN	Continue dosing Monitor liver panel weekly If ALT/AST fall to <1.5×ULN, stop weekly monitoring	

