ALT or AST ≥ 10×ULN, and Total and direct bili < 1.5×ULN, and INR < 1.3 ×ULN	Interrupt dosing Monitor liver panel weekly If ALT/AST fall to <5×ULN, restart dosing; if ALT/AST fall to <1.5×, stop weekly monitoring	If the event does not resolve in 4 weeks or recurs, consult medical monitor about discontinuing study medication
ALT or AST \geq 5×ULN, and Total or direct bili \geq 1.5×ULN, or INR \geq 1.3 ×ULN		Discontinue study medication
ALT or AST $< 5 \times ULN$, and Total or direct bili $\ge 1.5 \times ULN$, or INR $\ge 1.3 \times ULN$	Interrupt dosing Monitor liver panel weekly If total and direct bili fall to <1.5 ×ULN and/or INR falls to < 1.3× on 2 consecutive tests, stop weekly monitoring and restart dosing	If the event does not resolve in 4 weeks or recurs, consult medical monitor about discontinuing study medication

For patients with Gilbert Syndrome, the 1.5 × ULN criteria for total and direct bilirubin will be replaced with a 1.5 × ULN for direct bilirubin and there will be no monitoring criteria for total bilirubin [Fontana 2020]. Other etiologies of ALT, AST, total and direct bilirubin, and INR elevations, such liver injury induced by other drugs and other viral infections, should be ruled out and treated accordingly.

If a patient prematurely discontinues study medication on or before Day 169, the Day 169/Early termination procedures will be performed. Patients who prematurely discontinue study medication will remain in the study for follow-on study assessments.

Patients will be followed for 52 weeks after the last dose of study medication (504 days beyond Day 1 for patients who complete the 24-week Treatment Period). AEs and concomitant medications will be recorded from the signing of informed consent to Day 169, but only MAEs, NCIs, and IMCs, which will be categorized as AEs, will be followed subsequently. Likewise, concomitant medications will be recorded through Day 169, but only immunosuppressive medications, vaccines, and new HBV treatments or medications associated with MAEs, NCIs, SAEs, hepatitis flares, or hepatic injury will be recorded beyond this point. At the end of the clinical trial, the decision about follow-on treatments and medical care will be made by the patient's medical physician or medical team in accordance with the usual standard of care.

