6.4. Dosing Modifications

The sentinel cohort of 12 patients will undergo blinded safety review by the Safety Committee 7 to 10 days after all ongoing patients in the sentinel cohort have completed

the respective dose of study medication and will determine the decision to continue at that dose into the expanded cohort. Safety will be assessed in the sentinel cohort before each dose is administered to the expanded cohort. If any of the Stopping Rules in Section 7.1.1 are met in one or more patients in the sentinel cohort and the event(s) is deemed possibly or probably related to HepTcell, dosing will be suspended pending DMC review. DMC recommendations may include instituting modifications to ensure the safety of continued dosing or discontinuing the study. If none of the Stopping Rules (below) are met, randomization and dosing may continue in the expanded study cohort. Patients will be unblinded as necessary to assess the relationship between the study medication and events that meet criteria for Stopping Rules. Patients who experience events that meet criteria for Stopping Rules will permanently terminate dosing.

Monitoring and dosing rules for patients who experience liver abnormalities is described in Section 4.1.

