7.1.1. Stopping Rules

In consultation with the DMC, the following Stopping Rules will be applied:

- ALT or AST $\geq 10 \times ULN$
- INR ≥ 1.3
- Total bilirubin $\geq 1.5 \times \text{ULN}$ (excluding patients with Gilbert Syndrome)
- Direct bilirubin $\geq 1.5 \times \text{ULN}$ (for patients with Gilbert Syndrome)
- SAEs
- Severe systemic reactogenicity event (see Appendix 1)

If any of the Stopping Rules are met in one or more patients in the sentinel cohort (ie, the first 12 patients dosed) and the event(s) is deemed possibly or probably related to study medication, dosing will be suspended pending DMC review. Similar procedures will be

applied if 2 or more patients in the sentinel or expanded study cohort together experience Stopping Rules deemed possibly or probably related to study medication at any time during the 24-week Treatment Period. DMC recommendations may include instituting modifications to ensure the safety of continued dosing or discontinuing the study.

If the study is halted based on a DMC decision or safety concern, the trial will only be restarted after notification of the competent authority via a substantial amendment.

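### The liver dosing table (Protocol Section 4.1 and Study Summary) gives some panels conflicting instructions on weekly monitoring, on permanent versus temporary stopping, and on restart after a Stopping Rule value

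*Protocol*

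**What the plan says.** The table in Protocol Section 4.1 (same content in the Study Summary) has four rows, numbered here in order:

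- **Row 1:** ALT or AST 5 to <10×ULN, bilirubin and INR below threshold. Continue dosing, weekly panels.
- **Row 2:** ALT or AST ≥10×ULN, bilirubin and INR below threshold. Interrupt, weekly panels, restart once the enzymes fall below 5×ULN.
- **Row 3:** ALT or AST ≥5×ULN with total or direct bilirubin ≥1.5×ULN, or INR ≥1.3×ULN. Discontinue.
- **Row 4:** ALT or AST <5×ULN with the same bilirubin/INR condition. Interrupt, weekly panels. The release condition is "If total and direct bili fall to <1.5 ×ULN and/or INR falls to < 1.3× on 2 consecutive tests", and the action is to "on 2 consecutive tests, stop weekly monitoring and restart dosing".

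Rows 2 and 4 share a backstop: "If the event does not resolve in 4 weeks or recurs, consult medical monitor about discontinuing study medication".

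Three other rules bear on the same patients. Section 4.1 sets a check before each dose. Its first item is "confirmation that patients did not meet a Stopping Rule (Section 7.1.1"), and its second requires liver values to be acceptable under this table. Section 7.1.1 lists the Stopping Rules: ALT or AST ≥10×ULN, INR ≥1.3, total bilirubin ≥1.5×ULN (direct bilirubin instead in Gilbert patients), SAEs, and severe systemic reactogenicity. Section 6.4 states: "Patients who experience events that meet criteria for Stopping Rules will permanently terminate dosing". SAP Section 5.3.16 repeats that sentence.

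**The concern.** A liver-safety table used at about 35 centres should give one instruction per panel. This one does not, in three places.

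1. **Row 4 release.** Entry is on bilirubin *or* INR. Release is on bilirubin *and/or* INR, which includes *or*. The row can therefore tell a site both to stop weekly panels and to continue them.
2. **Rows 3 and 4.** Nothing says which enzyme governs when ALT and AST fall on opposite sides of 5×ULN. One site may end treatment permanently where another interrupts and later restarts.
3. **Restart.** Rows 2 and 4 provide for restart after recovery, but most values that put a patient there are themselves Stopping Rule values, for which Sections 4.1 and 6.4 bar further dosing.

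At stake are consistent patient protection and consistent conduct across sites. No efficacy analysis depends on it.

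**Working it through.** The plan gives no figure to reproduce. The check enumerates panel types; the counts are types, not patient frequencies.

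**Inputs** (Protocol 4.1 and 7.1.1). ALT and AST each take three bands (<5, 5 to <10, ≥10×ULN), giving 3 × 3 = 9 pairs. Total bilirubin, direct bilirubin and INR are each normal or raised, giving 2³ = 8 patterns, 7 of them abnormal. For Gilbert patients only direct bilirubin and INR count: 2² = 4 patterns, 3 abnormal. The grid is 9 × 8 = 72 types (Gilbert 9 × 4 = 36). Rows 3 and 4 are read as enzyme condition AND (bilirubin OR INR). INR ULN is assumed to be at least 1.0, so that INR ≥1.3×ULN implies INR ≥1.3.

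**Row 4 release.** Patterns with both bilirubin and INR raised: total+INR, direct+INR, all three = 3 of 7 (Gilbert 1 of 3). For these:

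| Bilirubin recovered | INR recovered | Literal *or* releases | Still meets row 4 entry |
|---|---|---|---|
| no | no | no | yes |
| yes | no | yes | yes |
| no | yes | yes | yes |
| yes | yes | yes | no |

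Two of the three unresolved states are released and re-entered on the same result. All the exposed patterns include raised INR, a Stopping Rule value, so the first pre-dose item blocks the dose. What is left in doubt is weekly monitoring.

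**Rows 3 and 4 together.** One enzyme ≥5×ULN and the other <5×ULN: 4 of the 9 pairs.

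- Non-Gilbert: 4 × 7 = 28 of 72. Two of the four pairs include ≥10×ULN, so 2 × 7 = 14 are Stopping Rule types. In the other two pairs, 6 of 7 patterns have raised INR or total bilirubin, so 2 × 6 = 12 more. Total 26. The 2 left are isolated direct bilirubin with one enzyme 5 to <10×ULN.
- Gilbert: 4 × 3 = 12 of 36, all Stopping Rule types.

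Example: ALT 6×ULN, AST 3×ULN, total bilirubin 2×ULN meets row 3 through ALT and row 4 through AST.

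Keying to the higher enzyme reduces these overlaps to 0, but only with the brackets. If the wording is parsed as (enzyme AND bilirubin) OR INR, raised INR alone meets both rows, and 9 × 4 = 36 of the 72 types stay in both even after re-keying.

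**Restart rows after keying to the higher enzyme.**

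- Row 2: pairs with at least one enzyme ≥10×ULN = 9 − 4 = 5, all Stopping Rule values.
- Row 4: both enzymes <5×ULN, 1 × 7 = 7 types. Six have raised INR or total bilirubin.
- Non-Gilbert total: 5 + 6 = 11 of 12. Gilbert: 5 of 5 plus 3 of 3 = 8 of 8.

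**INR thresholds.** The table uses 1.3×ULN; Section 7.1.1 uses an absolute 1.3. The documents give no ULN. If it were 1.0, 1.1 or 1.2 (assumption), the table threshold would be 1.30, 1.43 or 1.56. Above 1.0, there is a band that meets the Stopping Rule but not the table's INR criterion.

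**The case against.** **Row 4 has a sensible reading.** Whatever was raised must recover, which mirrors the *or* at entry. A careful site would probably apply it, but the text does not say it.

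**A lapse in monitoring is not established.** Scheduled liver panels are 28 days apart from Day 57 to Day 169, 63 days apart from Day 169 to Day 232, and 91 days apart thereafter. A reader might infer gaps of that length. The documents do not support this. The table applies whenever an abnormality is reported after dosing starts, so a panel still raised re-enters row 4, which orders weekly tests. The exposed patients also all have raised INR. If Section 6.4 ends their dosing, Table 1 footnote b moves them to visits timed from the last dose, so the treatment-visit interval would not describe them. What stands is a contradiction within the row.

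**No overlap panel permits a dose.** This is correct, and it includes the 2 isolated direct-bilirubin types. Rows 3 and 4 both withhold, and the second pre-dose item enforces the table. A reader might infer that a patient could be dosed with bilirubin or INR still raised; the pre-dose check rules that out. The permanent-versus-temporary difference remains.

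**Section 6.4 goes on to refer liver abnormalities to Section 4.1.** That could be read as letting the table govern. It does not settle the matter, because Section 4.1's own first pre-dose item bars patients who met a Stopping Rule. The conflict sits inside the section being pointed to.

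**Little practical effect now.** SAP Section 2 records that the study was terminated for lack of efficacy, with no significant safety events. This limits the value of an amendment but does not change what the text says.

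**Conclusion.** The point holds as a minor defect in safety-conduct wording. Row 4 contradicts itself on ending weekly monitoring in 3 of 7 abnormal bilirubin/INR patterns (Gilbert 1 of 3). Rows 3 and 4 give different dosing outcomes for 28 of 72 panel types (Gilbert 12 of 36). The restart instructions in rows 2 and 4 conflict with the Stopping Rule provisions in 11 of 12 types (Gilbert 8 of 8).

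The counts rest on the bracketed reading of rows 3 and 4 and on INR ULN being at least 1.0. The restart counts also assume keying to the higher enzyme. Inclusion Criterion 6 requires essentially normal liver tests at screening, so few patients should reach these rows. Backstops also exist: the medical-monitor consult, AE follow-up until resolution or stabilisation for abnormalities judged clinically significant (Sections 9.2 and 9.4), and the scheduled panels. Alpha, power and analysis are unaffected.

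**What to change.** In both copies of the table:

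- Key every row to the higher of ALT and AST as a multiple of ULN. This also removes the row 1/row 2 overlap (for example ALT 12×, AST 6×ULN), where the pre-dose check already withholds the dose.
- Write rows 3 and 4 as: enzyme condition AND (total or direct bilirubin ≥1.5×ULN OR INR ≥1.3×ULN).
- For row 4 release, require total and direct bilirubin <1.5×ULN AND INR below threshold on 2 consecutive tests (direct bilirubin only in Gilbert patients).
- Use one INR threshold in the table and in Section 7.1.1.

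In the same amendment, state which rule governs. The more protective choice is Section 6.4: delete row 2's restart and limit row 4's restart to isolated direct bilirubin in non-Gilbert patients. If the table is meant to govern, amend Section 6.4, SAP Section 5.3.16 and the first pre-dose item to allow restart after recovery.

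**Cost.** One table reworded in two places, the INR threshold aligned, and the related sentences edited; no new scheduled visits and no change to sample size or analysis. The downside is that overlap panels move to discontinuation. If Section 6.4 governs, this newly changes 2 non-Gilbert types. If the table governs, it changes up to 28 non-Gilbert and 12 Gilbert types. With the study terminated, the practical steps are to correct the table before any reuse and to check whether any patient with such a panel was handled inconsistently.

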4.2. Study Schematic

Each patient will participate in the study up to approximately 77 weeks (a 5--week Screening Period, a 24-week Treatment Period, and a 52-week Follow-up Period commencing after the last dose of study medication at Week 20).

Figure 1: Study Visits and Treatments

4.3. Rationale for Study Design

The study design replicates the general design of the prior Phase 1 study but extends treatment from 3 to 6 doses and the follow-up after the last dose of study medication from 30 to 52 weeks. These modifications will enhance the effects of study medication and provide a more extended follow-up to assess the durability of immunogenicity and AEs. Diaries will be collected for reactogenicity events at visits on Days 8 and 36, which correspond to 7±2 days after the first and second dose of study medication. A visit consisting of a targeted physical examination will be conducted 7±2 days after administration of Doses 1 and 2 of study medication. Safety laboratory testing (Table 3), including liver panel, for Doses 1 and 2 will be obtained during the visits conducted 7±2 after these doses of study medication. Safety laboratory for Doses 3, 4 and 5 will be obtained in the pre-treatment interval from 7 days after dose administration through the time that the next dose of study medication is administered. Safety labs after Dose 6 will be assessed at the Day 169 visit. Investigators will review the eligibility of all patients prior to dosing to determine if the next treatment is to be administered. Eligibility for the next treatment will include: 1) confirmation that patients did not meet a Stopping Rule (Section 7.1.1); 2) confirmation that the pre-treatment liver parameters are within acceptable ranges for treatment (Section 4.1); 3) confirmation that patients do not have a new confirmed or suspected IMC (Appendix 2). If abnormalities of ALT, AST, total bilirubin, direct bilirubin, or INR are reported after dosing is commenced, the monitoring and dosing rules of Section 4.1 will be applied. These procedures are considered sufficient to evaluate reactogenicity events, particularly after Doses 1 and 2, and guard

against hepatitis flares and liver function abnormalities that would preclude the scheduled administration of the next dose of study medication.

For most vaccines, reactogenicity is typically experienced within 3 days of vaccination, commensurate with the innate immune response. Because distinct and separate antigens are targeted, no specific interactions or immunological interferences between COVID-19 vaccines and HepTcell are otherwise anticipated. Therefore, if an authorized COVID-19 vaccine has been administered in proximity to a scheduled investigational product (IP) administration, $a \pm 3$ day window is allowed for IP dosing (Table 1). A COVID-19 vaccine given to a trial subject will be considered as a simple concomitant medication.

The grading of AE severity is described in Section 9.3.1. The US Food and Drug Administration Toxicity Grading Scale for Healthy Adult and Adolescent Volunteers Enrolled in Preventive Vaccine Clinical Trials [United States Food and Drug Administration 2007] will be the primary scale used to grade AE severity. This scale is being employed because the study population is anticipated to be relatively healthy and the proposed scale is felt to be better reflective of a healthy population that participates in vaccine trials. This scale also offers more detailed grading criteria for local reactogenicity events, particularly those for which measurement offers better characterization of the event

The study design adheres to the 2020 US Food and Drug Administration (FDA), European Medicines Agency (EMA), Health Canada and Medicines Health products Regulatory Agency (MHRA) guidances on the conduct of clinical trials during the COVID-19 pandemic [United States Food and Drug Administration 2020, European Medicines Agency 2020, Health Canada 2020, Medicines and Healthcare products Regulatory Agency 2021]. To that end, the minimal number of in-person clinic assessments deemed necessary for the safety and protection of patients are being undertaken, with home, work and telemedicine visits being conducted whenever possible. The risks and methods to minimize the risks of COVID-19 will be discussed with each patient, and changes in the risks of clinical trial tasks that occur as a result of changes in local circumstances will be assessed during the trial and communicated to patients on an ongoing basis. Study participants will not be prevented from receiving COVID-19 vaccines during their trial participation and will be advised accordingly.

4.4. Rationale for Study Population

Patients with inactive CHB and low HBsAg are likely to represent a population of patients more likely to benefit from immunotherapy than the population in Study FP02.2_CS_01, who could only achieve viral suppression through the use of nucleoside analogues. Inactive CHB patients have relatively low circulating levels of HBV DNA and are already demonstrating intrinsic immune control, albeit incomplete, over the virus. T cell responses against HBV antigens have also been shown to be inversely associated with serum HBsAg level, with lower levels leading to higher rates of spontaneous HBsAg serologic clearance [Loggi 2013]. In two studies of patients with inactive CHB treated with IFN-α therapy, the HBsAg cutoffs predicting HBsAg serologic clearance were 71 and 200 IU/mL, respectively [Lim 2019, Cao 2017]. In a metanalysis

of effects of patients treated with IFN- α , baseline qHBsAg levels predicted functional cure [Song 2021]. After 48 weeks of therapy, the HBsAg clearance rates were 92% (95% CI: 79% - 99%) for HBsAg <10 IU/mL, 88% (95% CI: 77% -95%) for <20 IU/mL, 73% (95% CI: 62% - 83%) for <100 IU/mL, 60% (95% CI: 48% - 71%) for <500 IU/mL, and 39% (95% CI: 25% - 53%) for <1000 IU/mL. While it is clear that clearance of HBsAg is predicted by baseline levels in these studies, there is minimal change in levels between 100 and 500 IU/mL (13%), and the most significant drop-off in HBsAg clearance is in those with qHBsAg >1000 IU/mL (34%). These observations support the recruitment of a well-defined subpopulation of inactive CHB patients with low qHBsAg levels to enhance anti-HBV immune responses and increase HBsAg loss rates. The provision for allowing the participation of patients with any one HBsAg level within the eligible range (qHBsAg \geq 10 IU/mL but \leq 200 IU/mL) within the past 12 months is to account for the variability in the quantitative HBsAg assay.

Patients with inactive CHB and over the age of 65 have also been excluded, as they would not be candidates for treatment of their condition in routine clinical practice. There is a global epidemic of obesity and those with hepatitis B are at risk for hepatic steatosis from nonalcoholic fatty liver disease (NAFLD). The risk and prevalence of NAFLD amongst those with HBV appears to be similar as the general population, ranging 17-30% [Shi 2021]. Inclusion of these subjects in the current study is allowed provided there is radiologic evidence of fatty liver or a Fibroscan consistent with hepatic steatosis and no evidence of active CHB (i.e., HBV DNA ≥2000 IU/mL) or other forms of liver disease.

The level of effectiveness and timeframes for contraception use for study eligibility comply with the guidelines of the Clinical Trial Facilitations Group recommendation related to contraception and pregnancy testing in clinical trials [Clinical Trial Facilitation Group 2014]. The fluoropeptides and IC31 of HepTcell are designed to form a local depot at the site of injection, and the magnitude and period of systemic exposure are anticipated to be limited. The high molecular weight peptides that comprise HepTcell present a low risk of passive transmembrane penetration and/or systemic exposure and it is unlikely that they will be absorbed vaginally or placentally. Peptides are expected to be degraded into smaller peptides and individual amino acids by the protein degradation pathways that are well understood. Even if systemic exposure to HepTcell were to occur, the fluoropeptides and IC31 adjuvant components would be rapidly metabolized and their appearance in semen would be limited, as would their appearance in plasma from semen. Any T cells stimulated by HepTcell would also be HBV specific and unable to cross the placenta. Therefore, one-month period of pregnancy testing after the last dose of study medication is considered sufficient to protect patients or their sexual partners who become pregnant after the 6 doses of study medication are administered.

